8.5 Additional Efficacy Analyses

Additional endpoints defined in Section 3.3 will be summarized at scheduled time points.

Additional Efficacy Analyses for Induction Period

For additional binary endpoints, point estimate and 95% CI using normal approximation will be provided for the response rate of the ravagalimab group using NRI-C and AO data.

For additional continuous endpoints, the LS-mean and 95% CI will be reported for the ravagalimab group using MMRM model and ANCOVA model based on AO data with baseline corticosteroid use (yes vs no) and baseline Mayo endoscopic sub-score (2 vs 3) as the fixed factors and the corresponding baseline value as the covariates.

For selected additional binary endpoints, point estimate and 95% CI using normal approximation will be provided for the response rate of ravagalimab and matched placebo group. Point estimate, 95% CI and p-value will be provided for the treatment comparison between ravagalimab and the matched placebo group based on the CMH test adjusting for baseline corticosteroid use (yes vs no) and Mayo endoscopic sub-score (2 vs 3).

For selected additional continuous endpoints, the LS mean and 95% CI will be reported for ravagalimab and matched placebo group. The LS mean treatment difference and associated 95% CI and p-values between ravagalimab and matched placebo group will be provided using MMRM model. For the MMRM analysis, data collected at or after UC-Related corticosteroids intercurrent event will be excluded. Supplementary analysis will be conducted based on ANCOVA model using AO data, with treatment, baseline corticosteroid use (yes vs no) and baseline Mayo endoscopic sub-score (2 vs 3) as the fixed factors and the corresponding baseline value as the covariates.

Additional Efficacy Analyses for Maintenance Period

Descriptive statistics will be provided for the ravagalimab group. These include the number of observations, mean, standard deviation, 95% CI, median, minimum, and maximum for continuous endpoints using AO data; and frequencies and percentages with 95% CI using normal approximation for binary endpoints using AO data.

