### 2.1 Individual Treatment Period Visit Activities

---

This section presents a list of activities performed during each visit, organized by visit. The dot pattern on the upper right indicates the place of the visit in the overall Treatment Period Activity Schedule.

Activities are grouped by category (Interview, Exam, etc.). Further information about each activity is provided in Section 2.1, which contains the definitions of superscript text.

Hospitalization and UC-related surgery will be captured as a part of supplemental Health Care Resource Utilization (HCRU) form of adverse event (AE) collection in electronic data capture (EDC) for the entire study.

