3.3 Additional Efficacy Endpoints

Additional efficacy endpoints are:

- Change from Baseline in modified Baron score over time (at visits with endoscopy)
- Achievement with stool frequency subscore (SFS) = 0, rectal bleeding subscore (RBS) = 0, and Mayo endoscopic subscore = 0 over time (at visits with endoscopy)
- Time to clinical response per Partial Adapted Mayo score
- Endoscopic improvement over time (at visits with endoscopy)
- Clinical remission per Adapted Mayo score over time (at visits with endoscopy)
- Clinical response per Adapted Mayo score at over time (at visits with endoscopy)
- Clinical remission per Partial Adapted Mayo score over time
- Clinical response per Partial Adapted Mayo score over time
- Clinical remission per Adapted Mayo score over time among subjects who were taking corticosteroids at Baseline and subsequently discontinued corticosteroids for \geq 90 days prior to the respective visit
- Discontinuation of corticosteroid use for subjects taking corticosteroids at Baseline at all visits over time
- Endoscopic remission over time (at visits with endoscopy)
- Clinical remission per Full Mayo score over time in subjects with a Full Mayo score of 6 to 12 at Baseline (at visits with endoscopy)
- Clinical response per Full Mayo score over time in subjects with a Full Mayo score of 6 to 12 at Baseline (at visits with endoscopy)

- Achievement of SFS ≤ 1 over time
- Achievement of RBS = 0 over time
- Change from Baseline in RBS over time
- Change from Baseline in SFS over time
- Change from Baseline in fecal calprotectin (FCP) over time
- Change from Baseline in high sensitivity C-reactive protein (hs-CRP) over time
- Change from Baseline in Inflammatory Bowel Disease Questionnaire (IBDQ) over time
- UC-related Hospitalizations (yes/no) over time
- UC-related surgeries (yes/no) over time
- No bowel urgency over time
- Change from Baseline in weekly abdominal pain score over time
- Achievement of $\geq 30\%$ reduction from Baseline in weekly abdominal pain score over time
- Achievement of Weekly abdominal pain score = 0 over time
- Change from Baseline in number of extraintestinal manifestations (EIM) over time (as captured in the EIM electronic case report form [eCRF])
- Histologic remission over time (at visits with endoscopy)
- Mucosal healing (endoscopic and histologic remission) over time (at visits with endoscopy)

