8.0 Efficacy Analyses

8.1 General Considerations

UC-Related corticosteroids intercurrent events are defined as follows:

- subjects not on UC-related corticosteroids (systemic or locally acting corticosteroids for UC) at Baseline who initiated UC-related corticosteroids during the Induction Period;
- subjects on UC-related systemic corticosteroids at Baseline who had dosages increased to greater than the prednisone equivalent dose of corticosteroid at Baseline, or initiation of any rectal corticosteroids during the Induction Period regardless of rectal corticosteroid dose.

The time point of the UC-related corticosteroids intercurrent event is defined as the date when one of the scenarios above occurs for a subject. As such, subjects will be considered as "non-responder" for binary endpoints at or after the occurrence of the UC-related corticosteroids intercurrent event through the end of the Induction Period. For continuous endpoints, all measurements at or after the occurrence of the UC-related corticosteroids intercurrent event through the end of the Induction Period will not be used in the analysis.

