8.2 Handling of Missing Data

Missing data imputation will be done only for efficacy variables (categorical and continuous variables). For the analysis other than efficacy, no imputation will be done for missing values.

Censoring

For the time-to-event endpoint, i.e., time to clinical response per Partial Adapted Mayo score, missing data will be considered as censored at the last available time for the information.

Non-Responder Imputation incorporating Multiple Imputation to handle missing data due to COVID-19 (NRI-C)

The NRI-C will categorize any subject who does not have an evaluation during a pre-specified visit window (either due to missing assessment or due to early withdrawal from the study) as a non-responder for the visit. In addition, at or after the UC-related corticosteroids intercurrent event (see Section 8.1), subjects will be counted as non-responders. The only exception is that missing data due to COVID-19 infection or logistical restrictions related to the COVID-19 pandemic will be handled by Multiple Imputation (MI). At each visit, subjects will be characterized as responders or non-responders based on MI imputed values if missing due to COVID-19; otherwise, subjects will be considered as non-responders for missing due to other reasons in the NRI-C approach.

Mixed-Effect Model Repeated Measurements (MMRM)

MMRM analysis will be conducted using mixed-effect model including observed measurements at all visits. For the MMRM analysis, data collected at or after UC-Related corticosteroids intercurrent event will be excluded. The mixed model includes the categorical fixed effects of visit, baseline corticosteroid use (yes vs no), baseline Mayo endoscopic sub-score (2 vs 3), the continuous fixed covariate of baseline measurement and treatment and treatment-by-visit interaction, if applicable. An unstructured variance covariance matrix will be used. If there is a convergence issue, a compound symmetry structure and a variance components structure will be considered in sequence. The parameter estimations are based on the assumption of data being missing at random and using the method of restricted maximum likelihood (REML).

As Observed (AO)

The AO analysis will not impute values for missing evaluations, and thus a subject who does not have an evaluation on a scheduled visit will be excluded from the AO analysis for that visit. All observed data will be used in the analysis.

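### In the Induction Period, SAP 8.5 applies non-responder imputation to UC-related hospitalization and surgery, where the counted outcome is the bad event, so that estimate is wrong whichever way non-responder is coded

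*SAP*

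**What the plan says.** SAP 3.3 lists two adverse outcomes among the additional efficacy endpoints: "UC-related Hospitalizations (yes/no) over time" and "UC-related surgeries (yes/no) over time". Protocol 3.4 words both as the proportion of subjects who have the event.

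SAP 8.5 opens with "Additional endpoints defined in Section 3.3 will be summarized at scheduled time points". For induction it then states: "For additional binary endpoints, point estimate and 95% CI using normal approximation will be provided for the response rate of the ravagalimab group using NRI-C". The same sentence also names AO data. No endpoint is excepted. For the Maintenance Period it uses AO data only.

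SAP 8.2 defines NRI-C. It will "categorize any subject who does not have an evaluation during a pre-specified visit window" as a non-responder for that visit. The one exception is data missing because of COVID-19, which are multiply imputed. SAP 8.1 adds a steroid rule that 8.2 repeats: subjects become non-responders "for binary endpoints at or after the occurrence of the UC-related corticosteroids intercurrent event through the end of the Induction Period". This applies whether or not data were observed. Under AO, SAP 8.2 imputes nothing, leaves out subjects with no evaluation at the scheduled visit, and uses all observed data.

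The events themselves are not visit assessments. Section 2.1 of the Operations Manual (Protocol Appendix F) says: "Hospitalization and UC-related surgery will be captured as a part of supplemental Health Care Resource Utilization (HCRU) form of adverse event (AE) collection", and that this runs for the whole study.

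**The concern.** Non-responder imputation is conservative when the counted outcome is favourable, such as remission or endoscopic improvement, because an unknown or rescued subject is counted as a failure. For hospitalization and surgery the counted outcome is the failure, and the rule loses that property.

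The steroid rule is the more serious part because it overrides data that are in hand. Protocol 5.3 and 5.4 prohibit starting or increasing corticosteroids through Week 12, so a steroid intercurrent event probably marks worsening disease, which may also lead to admission. A subject admitted for UC and given steroids would have a known admission replaced by an imputed status.

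At stake is whether the Induction rates of two harm-type endpoints listed in the protocol can be interpreted. The primary analysis is not touched.

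**Working it through.** **No plan figure to reproduce.** The documents give no expected rate of UC-related hospitalization, surgery, missing evaluations or steroid intercurrent events. The check is therefore one of logic, with an assumed illustration.

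**Step 1: follow the rule to these endpoints.**
- SAP 8.5 covers every SAP 3.3 endpoint; hospitalization and surgery are in that list and are binary.
- The quantity reported is a response rate. Protocol 3.4 makes that the proportion with the event.
- On that literal reading a non-responder is a subject without the event. The SAP does not define responder or non-responder for these two endpoints, so the opposite coding (non-responder = unfavourable outcome) cannot be excluded.

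**Step 2: formulas.** N = 40 (SAP 2.4). Let k be the number of affected subjects (non-COVID missing evaluation, or steroid intercurrent event), a the number of them with an event that NRI-C overrides, and u the events among the other N − k.

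| Estimate | Formula | Error |
|---|---|---|
| Every event counted | (u + a)/N | none |
| NRI-C, non-responder = no event | u/N | −a/N |
| NRI-C, non-responder = unfavourable | (u + k)/N | +(k − a)/N |
| AO, all affected subjects observed | (u + a)/N | none |
| AO, all affected subjects lack the visit evaluation | u/(N − k) | depends on a and k |

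The literal coding is right only if no affected subject had an event (a = 0). The opposite coding is right only if all of them did (a = k).

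**Step 3: one assumed case,** k = 8, u = 2, a = 4.
- Every event counted: (2 + 4)/40 = 15.0%.
- NRI-C, literal: 2/40 = 5.0%.
- NRI-C, opposite: (2 + 8)/40 = 25.0%.
- AO: 6/40 = 15.0% if all 8 are observed; 2/32 = 6.3% if all 8 are missing.

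**Step 4: assumed range,** k = 4, 8 or 12; u = 1 or 2; a from 0 to k/2.
- Literal coding: shortfall a/40, from 0 to 6/40 = 15 percentage points. With k = 12, u = 1, a = 6, it gives 1/40 = 2.5% against 7/40 = 17.5%.
- Opposite coding: excess (k − a)/40, from 2/40 = 5 points (k = 4, a = 2) to 12/40 = 30 points (k = 12, a = 0). With k = 12, u = 2, a = 0, it gives 14/40 = 35.0% against 2/40 = 5.0%.

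The sign of the error thus depends on a coding that the SAP leaves open.

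**The case against.** The strongest reply is that this is a missing definition with little consequence. Several parts of it stand:
- A reader might infer that the plan biases the harm rates low and so flatters ravagalimab. The documents do not support that as a fact: the low direction follows only from the literal coding, which the SAP never confirms, and the other coding errs upward.
- A reader might also infer that the plan removes these events from the report. It does not. AO is reported beside NRI-C and keeps events observed after steroids. Hospital admission is a serious adverse event criterion (Protocol 6.1), serious events are tabulated and listed (SAP 9.2.5), and missing safety data are not imputed (SAP 9.1).
- COVID-19-related gaps go to multiple imputation, and the rule stops at the end of Induction.
- Because the events are collected outside visit assessments, a missed visit need not be a missing evaluation. Whether an event before the steroid date is carried forward to later visits depends on whether over time means cumulative or visit-specific, which is also unstated.
- These are two among many additional endpoints in a proof-of-concept study, and no decision rule uses them.

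This narrows the point without removing it. Neither coding gives a correct NRI-C rate outside the limiting cases in the working, so defining the term would not be enough. AO's exclusion of subjects without a scheduled-visit evaluation is the wrong test for events collected continuously. The serious adverse event tables are by system organ class and preferred term and do not give the UC-related proportion named in the protocol.

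**Conclusion.** Wrong as written, with low to moderate severity. For UC-related hospitalization and surgery in Induction, the NRI-C estimate replaces known outcomes after steroid start and assigns outcomes to subjects with non-COVID missing evaluations. The result is too low under the literal coding whenever an affected subject had an event, and too high under the opposite coding whenever an affected subject had none. The AO estimate avoids the steroid problem but not the visit-attendance problem.

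The size cannot be derived from the documents. The 0 to 15 point shortfall and the 5 to 30 point excess rest wholly on assumed counts (4 to 12 of 40 subjects affected, at most half of them with an event). They show what coding alone can do and do not forecast this trial. Only exploratory endpoints are affected.

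**What to change.** In SAP 8.5, exempt UC-related hospitalization and UC-related surgery from NRI-C and from the steroid rule in SAP 8.1. For each, report the number and percentage of FAS subjects with at least one observed event by each time point, taken from the adverse event and health care resource utilization data, regardless of steroid use or visit attendance. State the follow-up time for drop-outs; an exposure-adjusted rate could be added as a supplement. Keep NRI-C for endpoints whose counted outcome is favourable.

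The cost is one SAP paragraph and a small programming change. No new data are needed, since the events are already collected for the entire study.

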### Disease Activity

- ✓ 6. Diagnosis of UC for at least 3 months prior to Baseline. Appropriate documentation of biopsy results consistent with the diagnosis of UC in the assessment of the Investigator, must be available.
- ✓ 7. Subject meets the following disease activity criteria: Active UC with an Adapted Mayo score of 5 to 9 points and endoscopic subscore of 2 to 3 (confirmed by central review).
- ✓ 8. No current diagnosis of CD or inflammatory bowel disease-unclassified (IBD-U).
- ✓ 9. No extent of inflammatory disease limited to the rectum as assessed by screening endoscopy.
- ✓ 10. No currently known complications of UC such as:
  - fulminant colitis,
  - toxic megacolon,
  - previous colectomy (total or subtotal),
  - or any other manifestation that might require surgery while enrolled in the study
- ✓ 11. Subjects must not have an ostomy or ileoanal pouch.

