1.0 Introduction

This Statistical Analysis Plan (SAP) describes the statistical analyses for ravagalimab (ABBV-323) Study M15-722 Ulcerative Colitis (UC): Ravagalimab in Subjects with Moderately to Severely Active UC Who Failed Prior Therapy.

Study M15-722 examines the efficacy and safety of ravagalimab in subjects with moderately to severely active UC who failed prior therapy.

The analyses of pharmacokinetic and biomarker analyses will not be covered in this SAP.

The SAP will not be updated in case of administrative changes or amendments to the protocol unless the changes impact the analysis.

Unless noted otherwise, all analyses will be performed using SAS Version 9.4 (SAS Institute Inc., Cary, NC 27513) or later under the UNIX operating system.

This SAP includes changes to analyses described in the protocol. Details are outlined in Section [13.0](#).

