2.4 Sample Size Determination

The planned sample size is up to approximately 40 subjects.

Meta-analysis for historical placebo data from tofacitinib (OCTAVE1/2)¹, upadacitinib (Phase 2b; data on file) and ustekinumab (Stelara Phase 3 UNIFI)² studies gives [REDACTED] endoscopic improvement rate at Week 8. The matched prior distribution for placebo is [REDACTED]

[REDACTED] The prior for ravagalimab treatment group will be set to Jeffreys prior Beta (0.5, 0.5) as non-informative. The probability that the posterior probability of rate difference > 0 is larger than 90% is more than 90% if the endoscopic improvement rate difference is 25% between ravagalimab and historical placebo, given a sample size of 40 subjects for ravagalimab. If ravagalimab has the same endoscopic improvement rate of [REDACTED] as historical placebo, that probability is approximately [REDACTED]

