7.1 Demographics and Baseline Characteristics

Continuous demographic variables include

- Age (years),
- weight (kg),
- body weight – female (kg)

- body weight – male (kg)
- height (cm),
- height – female (cm)
- height – male (cm)
- body mass index (bmi) (kg/ m²).

Categorical demographic variables include

- sex (male, female),
- age (< 40, 40 - < 65, ≥ 65 years),
- ethnicity (Hispanic or Latino, not Hispanic or Latino)
- race (white, non-white),
- region (Europe, North America, or rest of world),
- tobacco user (current, former, never, unknown),
- alcohol user (current, former, never, unknown).

Continuous disease characteristics at baseline include

- full mayo score and its components (stool frequency, rectal bleeding, PGA and endoscopy subscores),
- partial mayo score,
- adapted mayo score,
- hs-CRP (mg/L),
- fecal calprotectin (mg/kg),
- albumin (g/L),
- UC disease duration in years,
- modified Baron score,
- UCEIS,
- Geboes score,
- number of extraintestinal manifestations.

Categorical disease characteristics include

- baseline steroid use (yes, no),
- baseline immunosuppressant use (yes, no),
- baseline aminosalicylates use (yes, no),
- prior exposure to biologic/JAK therapy for UC (1, >1)
- prior inadequate response/intolerance to biologic/JAK therapy for UC (1, > 1)
- prior exposure to biologic therapy for UC (1, >1),
- prior exposure to anti-TNF use for UC (yes, no),
- baseline hs-CRP (<=5mg/L, > 5mg/L),
- mayo endoscopic subscore (2, 3),
- adapted mayo score (<= 7, > 7),
- full mayo score (<= 9, > 9),
- disease duration (\leq 3 years, > 3 years),
- disease extent (left-sided, extensive/pancolitis, limited to rectum)

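### Single-arm LS-means for the additional continuous induction endpoints have no stated weighting, and the SAS default would not in general estimate the mean of the enrolled FAS

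*SAP*

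**What the plan says.** SAP 8.5, under the induction period, makes the one-arm adjusted mean the reported result for continuous endpoints: "the LS-mean and 95% CI will be reported for the ravagalimab group using MMRM model and ANCOVA model based on AO data". No treatment difference is involved in that sentence.

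The ANCOVA is specified "with baseline corticosteroid use (yes vs no) and baseline Mayo endoscopic sub-score (2 vs 3) as the fixed factors", with the endpoint's own baseline value as covariate. SAP 8.2 gives the MMRM a matching structure: "The mixed model includes the categorical fixed effects of visit, baseline corticosteroid use (yes vs no), baseline Mayo endoscopic sub-score (2 vs 3"), plus the baseline measurement, with treatment terms only where they apply.

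SAP 1.0 states that "all analyses will be performed using SAS Version 9.4 (SAS Institute Inc., Cary, NC 27513) or later". Neither document names an LS-mean option, a weighting or a reference population for the average over factor levels.

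The same part of SAP 8.5 summarises binary induction endpoints as plain response rates. It summarises maintenance-period continuous endpoints with raw descriptive statistics. Both of those follow the mix of subjects actually enrolled.

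**The concern.** An LS-mean is a model prediction for a reference population. In a two-arm model without treatment-by-factor interaction, the choice of reference cancels in the difference. In a one-arm summary it does not cancel, because the absolute value is the result. With class factors and no option named, SAS weights the levels equally. The reference population is then half steroid users and half subscore 3, whatever the trial enrols.

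Nothing in the design steers the mix to that point. The protocol's disease-activity criterion admits an "endoscopic subscore of 2 to 3 (confirmed by central review") without a quota, and steroid users and non-users are both eligible. SAP Appendix E lists both factors among the propensity covariates that must be included for clinical relevance, so the plan cannot presume that they have no effect.

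Ten endpoints in SAP 3.3 are exposed: modified Baron score, RBS, SFS, FCP, hs-CRP, IBDQ, abdominal pain, number of extraintestinal manifestations, UCEIS and UC-100. Under the default, the proportion with SFS of 1 or less and the mean change in SFS at the same visit would describe two different populations.

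**Working it through.** The plan gives no figure of its own to reproduce here.

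**Inputs**
- Sample size: "The planned sample size is up to approximately 40 subjects" (SAP 2.4).
- Two 2-level factors plus a baseline covariate (SAP 8.2 and 8.5).
- Shares p1 and p2 in one level of each factor: not in the documents. SAP 7.1 only tabulates the factors afterwards (for example "baseline steroid use (yes, no")). They are assumed below, over a range.
- Factor effects b1 and b2: not in the documents, so also assumed.

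**Point estimate.** With additive factors:

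LS-mean at equal weights − mean at observed margins = b1(0.5 − p1) + b2(0.5 − p2)

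- 70% at subscore 3, subscore effect 0.5 SD, steroid term nil: 0.5 × 0.20 = 0.10 SD in absolute size.
- 80% at subscore 3, same effect: 0.5 × 0.30 = 0.15 SD.
- A factor contributes nothing if it is split 50:50 or has no effect. The two terms can also cancel.

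**Precision.** For uncorrelated factors:

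SE ratio (equal weights / observed margins) = sqrt(1 + (0.5 − p1)²/(p1(1 − p1)) + (0.5 − p2)²/(p2(1 − p2)))

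The last column is 40 divided by the squared ratio.

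| Assumed mix | Terms under the root | Ratio | Equivalent N of 40 |
|---|---|---|---|
| 50 / 50 | 1 + 0 + 0 | 1.00 | 40 |
| 60 / 40 | 1 + 0.042 + 0.042 | 1.04 | 36.9 |
| 70 / 30 | 1 + 0.190 + 0.190 | 1.18 | 29.0 |
| 75 / 35 | 1 + 0.333 + 0.099 | 1.20 | 27.9 |
| 80 / 30 | 1 + 0.563 + 0.190 | 1.32 | 22.8 |
| 80 / 20 | 1 + 0.563 + 0.563 | 1.46 | 18.8 |

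The formula takes the shares as fixed. At 75/35, simulated trials of 40 in which the counts vary by chance give about 1.26 instead of 1.20. Correlation between the baseline covariate and the subscore adds a little: with R² = 0.3, the 70/30 ratio becomes 1.21.

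**Against the raw mean.** In a one-arm ANCOVA the observed-margin LS-mean equals the raw mean of the analysed subjects exactly; simulation confirmed this to rounding error. Its interval is narrower than the raw-mean interval because it conditions on the observed covariates. The raw-mean interval is therefore the fairer benchmark. Average 95% CI widths from 2000 simulated ANCOVAs at N = 40 follow, in residual-SD units. The assumptions are 0.5 SD for each factor effect and −0.3 SD per SD of baseline.

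| Counts in one level of each factor | Equal weights | Observed margins | Raw mean | Equal / raw |
|---|---|---|---|---|
| 20 and 20 | 0.635 | 0.635 | 0.690 | 0.92 |
| 16 and 24 | 0.663 | 0.635 | 0.688 | 0.96 |
| 12 and 28 | 0.755 | 0.636 | 0.686 | 1.10 |
| 8 and 32 | 0.944 | 0.636 | 0.681 | 1.39 |

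This comparison depends on how much the covariates explain. A second simulation used factor effects of −1.0 and +0.5, residual SD 2 and counts varying by chance. Equal weighting then cost about 1.04 against the raw mean at 60/40 and about 1.22 at 75/35.

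**The case against.** **The SAP does not prescribe 50:50 weights.** A reader might infer that it does, but equal weighting is a software default, and an analysis at observed margins would comply with the text as it stands. This objection holds: the defect is an unspecified weighting that silence leaves at the default.

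**Not every endpoint need be shifted.** A reader might infer that all ten estimates will miss the enrolled mean by a material amount. The documents give neither the mix nor the effects, so they do not support that. Single scenarios can mislead. With 75% at subscore 3, 35% on steroids and effects of −1.0 and +0.5, the shift is 0.25 + 0.075 = 0.325 on an enrolled mean of −2.575, or 13%. Reversing only the steroid sign gives 0.25 − 0.075 = 0.175, about 7% of that same mean.

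**The interval is not always too wide.** A reader might infer that it is always wider than 40 subjects support. Against the raw-mean interval this fails at 50/50 and can fail near 60/40, as the second table shows.

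**The consequence is limited.** The endpoints are additional ones in an exploratory proof-of-concept study, with no decision rule attached. The baseline mix will be tabulated, so imbalance will be visible. An equal-weight adjusted mean is also a recognised summary. All of this stands, and it lowers the severity. It does not supply a reason to prefer a hypothetical half-and-half population when the neighbouring summaries describe the enrolled one.

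**Conclusion.** The point holds as a minor one. Because a one-arm LS-mean is itself the reported result, its reference population has to be stated. If it is not, the SAS default will generally give something other than the enrolled FAS mean.

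The size depends on assumed mixes and effects. The loss of precision relative to observed margins runs from nothing at 50/50 to roughly 20% at 70/30 or 75/35, and 30% to 50% at 80/30 to 80/20. It is smaller, or absent, against the raw-mean interval at moderate mixes. The formulas assume additive, uncorrelated factors.

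Scope is confined to single-arm summaries of the additional continuous induction endpoints. Primary and secondary endpoints are binary, and maintenance uses raw descriptive statistics. The matched-placebo LS-mean difference does not depend on the weights when there is no treatment-by-factor interaction, and the SAP specifies none.

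**What to change.** Add to SAP 8.2 and 8.5 that single-arm LS-means are evaluated at the observed FAS baseline distribution of corticosteroid use and endoscopic subscore, from a reference dataset with one record per subject. In SAS this is the observed-margins (OM) option pointed at that dataset. Centring both indicators at their FAS means does the same. The one-record rule matters for the MMRM, because observed margins taken from the analysis data would weight subjects by their number of available visits.

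For the matched-placebo summaries, use one common set of margins for both arms; the difference is unchanged. Show the raw mean change with its 95% CI beside each single-arm LS-mean.

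The cost is one extra programming specification and a sentence or two in the SAP. The remaining drawback is that the observed-margin interval conditions on the observed covariates and so is narrower than the raw-mean interval, which is why both should be shown.

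### Maintenance response and remission rates are planned on observed cases only; adding a non-responder row beside them, as in induction, is a cheap improvement

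*SAP*

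**What the plan says.** SAP 8.5 treats the two periods differently. For additional binary endpoints in induction, a point estimate and 95% CI "will be provided for the response rate of the ravagalimab group using NRI-C and AO data". For maintenance, the plan is descriptive: "frequencies and percentages with 95% CI using normal approximation for binary endpoints using AO data".

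SAP 8.2 defines AO as making no imputation, so that "a subject who does not have an evaluation on a scheduled visit will be excluded from the AO analysis for that visit". NRI-C, in the same section, counts a missing assessment or an early withdrawal as non-response. The exception is data missing because of COVID-19, which are multiply imputed.

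The maintenance period lasts 92 weeks and is meant to assess whether response is maintained (Protocol 4.1, SAP 2.2). Only Week 12 responders on the Partial Adapted Mayo score may enter. Protocol 5.5 lists lack of response among the reasons for stopping study drug or leaving the study, and it also lets a subject choose to leave after the Week 52 visit.

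**The concern.** A period that starts with responders asks one main question: who keeps the response? A subject who loses response and stops attending is part of the answer. Under AO that subject disappears from numerator and denominator alike, and the percentage is taken over those still being evaluated. If leaving is related to losing response, the AO rates at Week 52 and Week 104 come from a group selected partly on outcome, and they describe durability too favourably.

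The SAP guards against this in induction by pairing AO with NRI-C. It drops the pairing in the longer period, where more loss can accumulate, and gives no reason. At stake is how the durability rates are read, and whether a reader can see how much they depend on missing data.

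**Working it through.** **Step 1. Is NRI-C assigned to maintenance anywhere?**

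- Primary endpoint: Week 8; NRI-C (SAP 8.3.2), with AO as sensitivity (SAP 8.3.4).
- Secondary endpoints: Week 8 or Weeks 0 to 12 (SAP 3.2); NRI-C and AO (SAP 8.4).
- Additional binary endpoints, induction: NRI-C and AO (SAP 8.5).
- Additional binary endpoints, maintenance: AO only (SAP 8.5).
- Protocol 7.3 names NRI-C for the primary endpoint and leaves the rest to the SAP.

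No section assigns it. The plan states no figure for maintenance rates, so there is none to reproduce.

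**Step 2. Which endpoints are affected?** SAP 3.3 lists 20 binary endpoints. Two, UC-related hospitalization and surgery, are adverse outcomes and fall outside this point. The other 18 are achievements: response, remission, symptom, steroid-discontinuation and histology endpoints. Four of the 18 are restricted to a subgroup: two concern Baseline corticosteroid users (for example "Discontinuation of corticosteroid use for subjects taking corticosteroids at Baseline at all visits over time") and two concern Full Mayo scores (for example "Clinical remission per Full Mayo score over time in subjects with a Full Mayo score of 6 to 12 at Baseline").

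**Step 3. How far apart can the rows be?** Let N be the entrants in the endpoint's population, m those evaluated, r the responders, and d = 1 − m/N. Of the N − m unevaluated, c are missing because of COVID-19 and imputed at mean rate q; f = c/(N − m).

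- AO = r/m
- plain NRI = r/N
- NRI-C = (r + c·q)/N

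With c = 0, NRI = AO × (1 − d), so AO/NRI = 1/(1 − d). The documents give no d. For an assumed AO rate of 60%:

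| Assumed d | AO/NRI | AO | NRI |
|---|---|---|---|
| 10% | 1.11 | 60% | 54% |
| 30% | 1.43 | 60% | 42% |
| 50% | 2.00 | 60% | 30% |

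With assumed counts N = 20, m = 15 and r = 9, AO is 9/15 = 60.0% (normal-approximation 95% CI 35.2 to 84.8) and NRI is 9/20 = 45.0% (23.2 to 66.8).

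**Step 4. Is AO always the higher row?** No. AO − NRI-C = d × (AO − f·q), so NRI-C exceeds AO when f·q is greater than the AO rate. In the same example, 2 of the 5 unevaluated imputed at q = 60% give (9 + 1.2)/20 = 51%. All 5 imputed at q = 80% give (9 + 4)/20 = 65%, above AO.

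**Step 5. Which row is nearer the truth?** With c = 0, let p be the response rate among the unevaluated. Then AO − true = d × (AO − p), and NRI − true = −d × p. At d = 30% and AO = 60%:

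- p = 20%: AO is 12 points too high, NRI 6 points too low.
- p = 60%: AO is exact, NRI 18 points too low.

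The errors are equal in size at p = AO/2, here 30%. Below that NRI is nearer; above it AO is.

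**The case against.** The strongest case is that this is a coherent descriptive plan. Maintenance has no comparator and no test, the endpoints are labelled additional, and the study is a proof of concept without multiplicity control. AO is also used for the continuous maintenance endpoints. Non-responder imputation has its own bias: Step 5 shows it 18 points low where AO is exact, and counting a subject who chooses to leave after Week 52 as a failure is hard to defend as the better estimate. Stopping study drug is not the same as being unevaluated. Protocol 5.6 asks that such subjects keep attending scheduled visits unless they withdraw consent, and the maintenance premature-discontinuation visit includes endoscopy and Mayo scores (Operations Manual 2.1 and 3.15). Every size quoted above is assumed.

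Most of this stands, and it keeps the point minor. It argues against replacing AO; it does not argue against showing a second row. Continued follow-up does not cover withdrawn consent or missed visits. The disposition summary in SAP 5.0 shows how many stopped study drug, but gives no response rate that accounts for them.

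Two further inferences about corticosteroids are tempting but unsupported. A reader might infer that the SAP leaves open how maintenance data are used once Protocol 5.4 permits new or increased corticosteroids. It does not: the AO definition uses all observed data, and SAP 8.5 assigns AO to maintenance. A reader might also see a conflict because SAP 8.2 says that "at or after the UC-related corticosteroids intercurrent event (see Section 8.1), subjects will be counted as non-responders" without an end date. That sentence points to SAP 8.1, which sets the limit: "at or after the occurrence of the UC-related corticosteroids intercurrent event through the end of the Induction Period". The cross-reference removes the conflict.

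**Conclusion.** The point holds as a minor one. The only planned maintenance response and remission rates use AO alone, and they are likely too high if unevaluated subjects respond less often than evaluated ones. That condition is plausible, because lack of response is a listed reason to leave, but the documents do not establish it.

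The size is unknown. Under the assumptions of no COVID-19-related gaps and 10% to 50% unevaluated, an AO rate of 60% corresponds to a non-responder rate of 54% to 30%.

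A reader might go further and infer that AO must exceed NRI-C, or that NRI-C would give the correct rate. Steps 4 and 5 show that neither follows. Nor does the point reach the Week 8 primary analysis, which uses NRI-C.

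**What to change.** In SAP 8.5, keep the AO row and add an NRI-C row beside it for the 18 achievement-type maintenance endpoints. Name plain NRI, labelled as such, as the fallback if the imputation cannot be fitted. Leave out UC-related hospitalization and surgery.

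State the denominator at each visit: subjects in the efficacy population who entered maintenance and belong to the endpoint's population as SAP 3.3 defines it. Two items need a sentence each:

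- Say whether subjects randomized to placebo before Version 4.0 who entered open-label maintenance are counted. SAP 4.0 can be read either way: it admits anyone with at least one ravagalimab dose, then refers to those randomized to and receiving it.
- Say which denominator is intended for steroid-free remission: all Baseline corticosteroid users, or only those who have also been off corticosteroids for at least 90 days. SAP 3.3 does not settle this, and the added row should not redefine the endpoint by default.

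No new data are collected and permitted treatment is unchanged. The cost is SAP text, an imputation model usable through Week 104 (SAP 8.2 does not specify one), and one more row per endpoint and visit. Imputation may be unstable in so small a group: with an assumed 20 entrants, each imputed subject can move the rate by up to 1/20, or 5 points. The added row can also be too low, especially at Week 104 because of voluntary exits after Week 52. The SAP should therefore say that the two rows are read together as showing dependence on missing data.
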